#### Criteria for Evaluation:

**Efficacy:** Efficacy assessments will consist of evaluations for tumor progression using Response Evaluation Criteria in Solid Tumors (RECIST) v1.1 and will be based on a Central Radiographic Assessment Committee (CRAC) review of medical images, as outlined in the Schedule of Assessments. Additionally, efficacy will be assessed by overall survival.

Pharmacokinetic: Serum concentrations of rovalpituzumab tesirine ADC and the presence of antitherapeutic antibodies (ATA) will be determined.

**abbyie** Rovalpituzumab Tesirine M16-298 Protocol Amendment 4 EudraCT 2016-003503-64

#### **Criteria for Evaluation (Continued):**

Biomarkers: Pharmacodynamic and predictive biomarker assessments will include analyses of tumor material and circulating tumor cells for DLL3 expression, blood samples for inflammatory, tumor, and soluble markers. Samples may also be used for other nucleic acid or protein based exploratory biomarkers to understand the sensitivity or resistance to royalpituzumab tesirine and biology of SCLC.

Safety: Safety assessments include physical exam, vital signs, body weight, ECOG score, clinical adverse events, laboratory tests (hematology, serum chemistries, urinalysis, and coagulation), ECGs, echocardiogram, fluid retention questionnaire, radiographic images review for fluid retention, and monitoring of concomitant medications.

#### Patient Reported Outcome (PRO):

Changes in the patient reported outcomes (PROs) EORTC QLQ-C30, EORTC QLQ-LC13, and EO-5D-5L from baseline will be assessed.

#### **Statistical Methods:**

#### Efficacy:

Progression-free survival (PFS) per CRAC and overall survival (OS) in patients with DLL3high ED SCLC are the two primary efficacy endpoints. To meet global regulatory requirements, a multiple testing strategy will be implemented to control the family-wise type I error (alpha) for comparisons of rovalpituzumab tesirine arm versus placebo arm with respect to progression-free survival (PFS) per CRAC in DLL3high patients, overall survival (OS) in DLL3high patients, PFS per CRAC in randomized patients, OS in randomized patients, and physical functioning scale score (EORTC QLQ-C30) in the randomized set.

The following null hypotheses are considered:

Two hypotheses in  $H_{01}$  are  $H_{01a}$  and  $H_{01b}$ .

 $H_{01a}$ : Rovalpituzumab tesirine arm is not superior to placebo arm in PFS per CRAC in DLL3high set.

H01b: Royalpituzumab tesirine arm is not superior to placebo arm in OS in DLL3high set.

H02: Rovalpituzumab tesirine arm is not superior to placebo arm in OS in randomized set.

H03: Royalpituzumab tesirine arm is not superior to placebo arm in PFS per CRAC in randomized set.

H04: Royalpituzumab tesirine arm is not superior to placebo arm in physical functioning scale score (EORTC QLQ-C30) in randomized set.

The null hypotheses will be tested in a fixed sequence of  $\{H_{01a}, H_{01b}, H_{02}, H_{03}, \text{ and } H_{04}\}$  in order. To maintain the family-wise type I error for the study, the null hypotheses in H01 (H01a and H01b) will be first tested with an alpha-split approach. The one-sided alpha of 0.25% and 2.25% will be assigned for PFS and OS hypothesis in H01, respectively. Out of one-sided alpha of 2.25% allocated to OS hypothesis  $(H_{01b})$ , the one-sided alpha of  $10^{-6}$  will be spent for the early look at the OS data for futility analysis. If the hypothesis for PFS in  $H_{01}$  ( $H_{01a}$ ) is rejected the one-sided alpha of 0.25% will be recycled to the OS hypothesis in H01 (H01b). Hence, the hypothesis for OS in H01 (H01b) will be tested either at a one-sided 2.4999% or one-sided 2.2499% level of significance depending on the PFS hypothesis in H01 a is rejected

If either PFS or OS endpoint reaches statistical significance, the study is considered positive. No further tests will be performed if the OS endpoint in DLL3high population (H01b) does not reach statistical significance.

Rovalpituzumab Tesirine M16-298 Protocol Amendment 4 EudraCT 2016-003503-64

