#### **Statistical Methods (Continued):**

The hypothesis in  $H_{02}$  will be tested if the hypothesis in  $H_{01b}$  is rejected. If the hypothesis in  $H_{02}$  is rejected, then, either (i) H03 and H04 will be tested sequentially if the PFS endpoint in DLL3high subjects (H01a) is also rejected or (ii) only H04 will be tested if the PFS endpoint in DLL3high subjects (H01a) is not rejected.

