#### Sample Size:

There are two primary efficacy endpoints for this study: Progression-free survival (PFS) based on the CRAC and overall survival (OS) in subjects with DLL3high ED SCLC. To maintain the overall 1-sided type I error at a 2.5% for this study, the type I error will be split, assigning 0.25% to progression-free survival and the remaining 2.25% to overall survival. However, the OS endpoint will be tested at a one-sided 2.2499% significance level as a one-sided alpha of 10^-6 will be spent for the early look at the OS data for futility analysis.

The sample size of the study is primarily determined by the analysis of OS. It is assumed, taking into account the expected patient population for the study, that median overall survival in the placebo and rovalpituzumab tesirine arm will be around 9 months and 13 months, respectively. The increase of median OS in rovalpituzumab tesirine arm corresponds to a hazard ratio of 0.69, i.e., a reduction in the hazard of death by 31%. With all these assumptions, a total of 319 deaths among subjects with DLL3high are needed to achieve a 90% power based on a log-rank test at a one-sided significance level of 0.022499. Assuming a 19-month accrual period and the last enrolled subject followed for 12 months, at least 480 subjects with DLL3high are expected to be randomized (240 subjects in each arm). A total of 740 subjects regardless of DLL3 expression level (including 480 subjects with DLL3 high) will enroll in the study, assuming an approximate prevalence of 65% for subjects with DLL3high. For one-sided significance level of 0.022499, it is projected that an observed hazard ratio of 0.799 or less, corresponding to a 2.3 months or greater improvement in median OS, would result in a statistically significant improvement in the primary analysis of OS.

The primary endpoints of OS and PFS in DLL3high patients will be analyzed at the same time after observing at-least 319 OS event. It is expected at approximately 420 PFS events will be observed at the time of the primary analysis.

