It is assumed, taking into account the expected patient population for the study, that median progressionfree survival for the placebo and rovalpituzumab tesirine arm will be approximately 3 months and 4.5 months, respectively. The increase of median progression-free survival in rovalpituzumab tesirine arm corresponds to a hazard ratio of 0.667. With all these assumptions, a total of 420 PFS events assessed by the CRAC for the subjects with DLL3high are needed to achieve a 91% power based on a logrank test at a one-sided significance level of 0.0025. It is projected that an observed hazard ratio of 0.760 or less, corresponding to approximately 1 month or greater improvement in median PFS, would result in a statistically significant improvement in the PFS.

abbyie Rovalpituzumab Tesirine M16-298 Protocol Amendment 4 EudraCT 2016-003503-64

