# 8.3 Type I Error Adjustment Procedure for Multiple Testing

To meet global regulatory requirements, a multiple testing strategy will be implemented to control the family-wise type I error (alpha) to one-sided 0.025 level for comparisons of

rovalpituzumab tesirine arm versus placebo arm with respect to progression-free survival (PFS) per CRAC in DLL3high set, overall survival (OS) in DLL3high set, PFS per CRAC in randomized set, OS in randomized set, and physical functioning scale score (EORTC QLQ-C30) in randomized set.

The following null hypotheses are considered:

Two hypotheses in  $H_{01}$  are  $H_{01a}$  and  $H_{01b}$ .

 $H_{01a}$ : Rovalpituzumab tesirine arm is not superior to placebo arm in PFS per CRAC in DLL3high set.

[figure not shown]
H01b: Rovalpituzumab tesirine arm is not superior to placebo arm in OS in DLL3high set.

H02: Rovalpituzumab tesirine arm is not superior to placebo arm in OS in randomized set.

H03: Rovalpituzumab tesirine arm is not superior to placebo arm in PFS per CRAC in randomized set.

H04: Rovalpituzumab tesirine arm is not superior to placebo arm in physical functioning scale score (EORTC QLQ-C30) in randomized set.

The null hypotheses will be tested in a fixed sequence of  $\{H_{01a}, H_{01b}, H_{02}, H_{03}, \text{ and } H_{04}\}$  in order. To maintain the family-wise type I error for the study, the null hypotheses in  $H_{01}$  ( $H_{01a}$  and  $H_{01b}$ ) will be first tested with an alpha-split approach. The one-sided alpha of 0.25% and 2.25% will be assigned for PFS and OS hypothesis in  $H_{01}$ , respectively. Out of one-sided alpha of 2.25% allocated to OS hypothesis ( $H_{01b}$ ), the one-sided alpha of  $10^{-6}$  will be spent for the early look at the OS data for futility analysis. If the hypothesis for PFS in  $H_{01}$  ( $H_{01a}$ ) is rejected the one-sided alpha of 0.25% will be recycled to the OS hypothesis in  $H_{01}$  ( $H_{01b}$ ). Hence, the hypothesis for OS in  $H_{01}$  ( $H_{01b}$ ) will be tested either at a one-sided 2.4999% or one-sided 2.2499% level of significance depending on the PFS hypothesis in  $H_{01a}$  is rejected or not.

[figure not shown]
Rovalpituzumab Tesirine M16-298 Protocol Amendment 4 EudraCT 2016-003503-64

[figure not shown]

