4.7 Type I Error Adjustment Procedures for Multiple Testing

To meet global regulatory requirements, a multiple testing strategy will be implemented to control the family-wise type I error (alpha) for comparisons of rovalpituzumab tesirine arm versus placebo arm with respect to progression-free survival (PFS) per CRAC in DLL3^{high} Set, overall survival (OS) in DLL3^{high} Set, PFS per CRAC in Randomized Set, OS in Randomized Set, and physical functioning scale score (EORTC QLQ-C30) in Randomized Set.

The following null hypotheses are considered:

H_{01a} : Rovalpituzumab tesirine arm is not superior to placebo arm in PFS per CRAC in DLL3^{high} Set.

H_{01b} : Rovalpituzumab tesirine arm is not superior to placebo arm in OS in DLL3^{high} Set.

H_{02} : Rovalpituzumab tesirine arm is not superior to placebo arm in OS in Randomized Set.

H_{03} : Rovalpituzumab tesirine arm is not superior to placebo arm in PFS per CRAC in Randomized Set.

H_{04} : Rovalpituzumab tesirine arm is not superior to placebo arm in physical functioning scale score (EORTC QLQ-C30) in Randomized Set.

[figure not shown]
The null hypotheses will be tested in a fixed sequence of $\{H_{01a}, H_{01b}, H_{02}, H_{03}, \text{ and } H_{04}\}$ in order. To maintain the family-wise type I error rate for the primary endpoints at 2.5%, the null hypotheses in H_{01} (H_{01a} and H_{01b}) will be first tested with an alpha-split approach. The one-sided alpha of 0.25% and 2.25% will be assigned to PFS and OS hypotheses in H_{01} , respectively. Out of the one-sided alpha of 2.25% allocated to OS hypothesis (H_{01b}), the one-sided alpha of 10^{-6} will be spent for the early look at the OS data for futility analysis. If the hypothesis for PFS in H_{01} (H_{01a}) is rejected, the one-sided alpha of 0.25% will be recycled to the OS hypothesis in H_{01} (H_{01b}). Hence, the OS hypothesis in H_{01} (H_{01b}) will be tested either at a one-sided 2.4999% or one-sided 2.2499% alpha level of significance depending on the PFS in H_{01} (H_{01a}) is rejected or not.

If either PFS or OS endpoint reaches statistical significance, the study is considered positive. No further tests will be performed if OS hypothesis in H_{01} (H_{01b}) does not reach statistical significance.

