The hypothesis in H_{02} will be tested if the hypothesis in H_{01b} is rejected. If the hypothesis in H_{02} is rejected, then, either (i) H_{03} and H_{04} will be sequentially tested if the PFS endpoint in DLL3^{high} Set (H_{01a}) shows statistical significance; or (ii) only H_{04} will be tested if the PFS endpoint in DLL3^{high} Set (H_{01a}) is not rejected.

Diagram of Hierarchical Testing of Primary and Secondary Endpoints is in [Figure 2](#).

Figure 2. Diagram of Hierarchical Testing of Primary and Secondary Endpoints¹

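### Alpha recycles from DLL3-high PFS to OS but never back, so a co-primary PFS result that misses 0.25% cannot be claimed even after OS and every later tested hypothesis is won: lost power, not a type I error fault

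*Protocol*

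**What the plan says.** The protocol synopsis, protocol 8.3 and SAP 4.7 give the same rule.

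- **Split.** "The one-sided alpha of 0.25% and 2.25% will be assigned for PFS and OS hypothesis in" the DLL3-high set. The purpose is stated as "To maintain the overall 1-sided type I error at a 2.5% for this study".
- **Futility look.** "the one-sided alpha of 10^{-6} will be spent for the early look at the OS data", taken from the OS share.
- **Recycling.** If DLL3-high PFS "is rejected the one-sided alpha of 0.25% will be recycled to the OS hypothesis in" that set, OS "will be tested either at a one-sided 2.4999% or one-sided 2.2499% level of significance depending on the" PFS result.
- **After OS.** H02 (OS, Randomized Set) follows H01b. If H02 is rejected and H01a was rejected, H03 (PFS, Randomized Set) and then H04 (physical functioning) are tested. Otherwise "only H_{04} will be tested if the PFS endpoint in DLL3^{high} Set (H_{01a}) is not rejected" (SAP); the protocol synopsis agrees: "only H 04 will be tested if the PFS endpoint in DLL3 high subjects (H 01a ) is not rejected".

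No sentence returns alpha from H01b, H02 or H04 to H01a, and 0.25% is the only level given for H01a. The sample-size text matches this: PFS significance is projected for "an observed hazard ratio of 0.760 or less". Protocol Figure 3 and SAP Figure 2, which diagram the procedure, are not visible in the available copies.

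**The concern.** PFS is one of two primary endpoints, yet it is held to one tenth of the overall alpha in exactly the case where the trial has succeeded on everything else it tested. A one-sided PFS p-value between 0.0025 and about 0.025 stays formally unsuccessful, and the alpha that H01b, H02 and H04 carried is discarded.

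Two consequences follow. H03 remains closed. And because both documents move the exploratory endpoints to the Randomized Set only if OS and PFS are significant there, that condition cannot be formally met on this path. The SAP cites a reference on graphical sequentially rejective procedures for its diagram; that framework is built for passing alpha on from rejected hypotheses. The plan uses it in one direction and gives no reason for stopping there.

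**Working it through.** **Inputs from the documents.** PFS: 420 events, assumed hazard ratio 0.667, one-sided 0.0025, stated power 91%. OS: 319 deaths, medians 9 and 13 months. Allocation 1:1. DLL3-high prevalence 65%. The text gives no separate levels for H02 to H04; I take them to inherit the OS level.

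**Reproducing the plan.** Critical HR = exp(-2z/sqrt(events)). With z = 2.807 and 420 events, exp(-5.614/20.494) = 0.760, as stated. Power = Phi(sqrt(420)/2 × |ln HR| - z) = Phi(10.247 × 0.405 - 2.807) = Phi(1.343) = 91.0%, as stated.

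**Level after a return.** 2.2499% + 0.25% = 2.4999%, so z = 1.960 and the critical HR is exp(-3.920/20.494) = 0.826. The band lost under the written rule is therefore about 0.761 to 0.826. It shifts with the event count: 0.755-0.822 at 400 events and 0.763-0.828 at 430.

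**Upper bound on the gain**, if the return were always reached: power goes from 91.0% to 98.6% at HR 0.667, and from 55.6% to 83.8% at HR 0.75.

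**Realistic gain.** H01b, H02 and H04 must all be won first. I simulated five correlated normal test statistics, one million draws per scenario. Assumptions: OS HR 9/13, H02 drift 0.9 of H01b, PFS-OS correlation 0.3-0.6, correlation sqrt(0.65) between DLL3-high and Randomized Set statistics for the same endpoint, and H04 correlation with the others 0-0.1. H04 power is not in the documents and is varied.

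| True PFS HR | As written | H04 power 5% | 16% | 84% |
|---|---|---|---|---|
| 0.667 | 91% | about 91.2% | about 91.5% | up to about 95% |
| 0.75 | 56% | about 56.5% | about 59% | up to about 74% |
| 0.78 | 40% | about 41% | about 44% | up to about 62% |

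**Does the return add family-wise error?** This can be argued without simulation.

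1. The return opens only after H01b, H02 and H04 are all rejected. If any of these is a true null, an error has already been made, so the return adds none.
2. If all three are false and H01a is a true null, any error requires rejecting H01a, because H03 is reached only through H01a. That probability is at most 2.4999%.
3. If H01a is also false and H03 is a true null, the only possible error is rejecting H03, tested at no more than 2.4999%.

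In case 2 the error rises from 0.25% to about 2.5%, which is the intended use of the alpha.

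**Does the existing branch rule hold 2.5%?** Not in every configuration. Take H03 and H04 as true nulls, very large OS effects, PFS-OS correlation 0.45 and H04 independent. Simulated family-wise error is about 3.5% at a true DLL3-high PFS HR of 0.907, 4.2% at 0.823 and 3.6% at 0.761, identical with and without the return. With OS effects near design it is about 3.7% at 0.823. The mechanism is visible at 0.823: H01a power is Phi(1.996 - 2.807) = 21%, so the H04-only route contributes about 0.79 × 2.25% = 1.8%. The other 2.4 points come from rejecting H03, which tends to happen in the same trials in which H01a is rejected.

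**The case against.** **This is an efficiency preference.** The rule is consistent in three places, conservative for H01a, and reflects a design in which OS drives the sample size. That stands: the plan is coherent and this is not an error in it. But the return comes last and takes nothing from any existing test, so no competing aim is protected by leaving it out.

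**The benefit may be small.** The trigger includes superiority over placebo in physical functioning. Protocol 3.5 reports pleural effusion in 33.9% and edema in 33.8% of subjects, so low H04 power is plausible; at 5% the gain at the design hazard ratio is about 0.2 points. That stands and limits the priority. On a 3-month placebo median the band is also clinically modest: 3/0.826 - 3 = 0.63 months to 3/0.760 - 3 = 0.95 months.

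**The figures might contain a return arrow.** They cannot be checked. If one does, it contradicts the text, and the two must be reconciled.

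**Stronger readings the documents do not support.** A reader might infer that one-way recycling inflates type I error, or that missing PFS makes the trial negative. Neither follows: leaving alpha unused cannot inflate error, and the plan calls the study positive on either primary endpoint, with the PFS hazard ratio, 95% interval and Kaplan-Meier results reported regardless. A reader might also infer that, with the return, family-wise error is 2.5% in every configuration. The check above shows otherwise, because of the existing branch rule.

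**Conclusion.** The point holds as a loss of power. When H01a misses 0.25% and H01b, H02 and H04 are all won, a PFS hazard ratio of roughly 0.761-0.826 cannot be formally claimed and H03 is not tested. The rule is exact; the limits are approximate because 420 events is only an expectation.

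With H04 power assumed at 5-84%, the return raises H01a power from 91% to about 91.2-95% at HR 0.667, from 56% to about 56.5-74% at 0.75, and from 40% to about 41-62% at 0.78. The larger gains need both a weaker PFS effect than designed and high H04 power.

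The return adds no family-wise error beyond 2.5%, whatever the correlations. The excess of about 3.5-4.2% belongs to the rule already written. It requires a DLL3-high PFS benefit offset in the remaining subjects, together with no H04 benefit, and its size rests on the assumed correlations and effect sizes. That configuration is unlikely, but strong control has to cover it.

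**What to change.** Before unblinding, add to branch (ii) in protocol 1.2 and 8.3 and in SAP 4.7:

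*If H01a was not rejected at one-sided 0.25% and H01b, H02 and H04 are all rejected, H01a is retested at one-sided 2.4999%. If it is then rejected, H03 is tested at one-sided 2.4999%.*

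Adjust the fixed-sequence sentence, which lists H01a only once at the start, and reconcile protocol Figure 3 and SAP Figure 2 with the new text. Do not add a statement that the whole procedure holds 2.5% in every configuration; the rule choosing between H03-then-H04 and H04 alone should be examined separately.

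**Cost.** The levels and power of H01b, H02 and H04 do not change, and no extra subjects or events are needed. The text change is short, but for the protocol it means an amendment with IEC/IRB approval before implementation (protocol 9.1), in a study of about 300 sites. The SAP part can be made before the SAP is finalized, which the plan already places before unblinding.

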#### **Statistical Methods (Continued):**

The hypothesis in  $H_{02}$  will be tested if the hypothesis in  $H_{01b}$  is rejected. If the hypothesis in  $H_{02}$  is rejected, then, either (i) H03 and H04 will be tested sequentially if the PFS endpoint in DLL3high subjects (H01a) is also rejected or (ii) only H04 will be tested if the PFS endpoint in DLL3high subjects (H01a) is not rejected.

## **Futility Analysis:**

Unblinded interim data will be analyzed and reviewed by the IDMC. A futility analysis will be conducted when approximately 160 deaths in subjects with DLL3 high ED SCLC (approximately 50% of the planned deaths) are observed. The trial may be stopped for futility if the estimated Overall Survival Cox HR of Rova-T to Placebo at this analysis exceeds 0.9. The one-sided alpha of 10^-6 will be spent for the early look at the efficacy data for futility analysis.

#### Sample Size:

There are two primary efficacy endpoints for this study: Progression-free survival (PFS) based on the CRAC and overall survival (OS) in subjects with DLL3high ED SCLC. To maintain the overall 1-sided type I error at a 2.5% for this study, the type I error will be split, assigning 0.25% to progression-free survival and the remaining 2.25% to overall survival. However, the OS endpoint will be tested at a one-sided 2.2499% significance level as a one-sided alpha of 10^-6 will be spent for the early look at the OS data for futility analysis.

The sample size of the study is primarily determined by the analysis of OS. It is assumed, taking into account the expected patient population for the study, that median overall survival in the placebo and rovalpituzumab tesirine arm will be around 9 months and 13 months, respectively. The increase of median OS in rovalpituzumab tesirine arm corresponds to a hazard ratio of 0.69, i.e., a reduction in the hazard of death by 31%. With all these assumptions, a total of 319 deaths among subjects with DLL3high are needed to achieve a 90% power based on a log-rank test at a one-sided significance level of 0.022499. Assuming a 19-month accrual period and the last enrolled subject followed for 12 months, at least 480 subjects with DLL3high are expected to be randomized (240 subjects in each arm). A total of 740 subjects regardless of DLL3 expression level (including 480 subjects with DLL3 high) will enroll in the study, assuming an approximate prevalence of 65% for subjects with DLL3high. For one-sided significance level of 0.022499, it is projected that an observed hazard ratio of 0.799 or less, corresponding to a 2.3 months or greater improvement in median OS, would result in a statistically significant improvement in the primary analysis of OS.

The primary endpoints of OS and PFS in DLL3high patients will be analyzed at the same time after observing at-least 319 OS event. It is expected at approximately 420 PFS events will be observed at the time of the primary analysis.

It is assumed, taking into account the expected patient population for the study, that median progressionfree survival for the placebo and rovalpituzumab tesirine arm will be approximately 3 months and 4.5 months, respectively. The increase of median progression-free survival in rovalpituzumab tesirine arm corresponds to a hazard ratio of 0.667. With all these assumptions, a total of 420 PFS events assessed by the CRAC for the subjects with DLL3high are needed to achieve a 91% power based on a logrank test at a one-sided significance level of 0.0025. It is projected that an observed hazard ratio of 0.760 or less, corresponding to approximately 1 month or greater improvement in median PFS, would result in a statistically significant improvement in the PFS.

abbyie Rovalpituzumab Tesirine M16-298 Protocol Amendment 4 EudraCT 2016-003503-64

